MRI data will be processed using adequate software such as SPM8, Freesurfer, Tortoise or DTI studio, to obtain, for each subject, images of gray and white matter, diffusion or perfusion maps. Images will then be compared using standard statistical parametric mapping software such as SPM, FSL, or AFNI, or even other more advanced programs as available. The statistical program will generate a group-specific adjusted mean value and an associated adjusted error variance for each voxel or region of interest that will be derived. Statistical significance may be established based on multiple-comparison corrections, permutations or simulations, in accordance with the analysis method selected. Data may be combined with other modalities and behavioral results. Accounting for multiple non-independent comparisons inherent in the analyses, a voxel level corrected P value < 0.05 will be used as the final threshold for significance. However, in line with functional imaging literature, results will also be reported as significant at a statistical threshold of $P < 0.001$, uncorrected, when a priori hypotheses require.

MRS data will be processed using specialized software packages such as LCModel, jMRUI or in house routines. These will be used to calculate ratios, such as GABA/Cr, NAA/Cr and, NAA/Cho. Anatomical images may be used to identify the ROI. Data may be combined with other modalities and behavioral results.

In case of group differences in severity of addiction or age due to randomization, we will add these variables as covariates to the analyses.

Plasma ghrelin

Weekly plasma ghrelin (total and acyl-ghrelin) will be analyzed using standard lab procedures [94]. Ghrelin levels will be compared between KD and SA group, and associated with weekly alcohol craving scores in both groups. We expect ghrelin to decrease in the KD versus SA group, and to be associated with the expected decreases in alcohol craving in KD.

b. Power analysis

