Empirical knowledge regarding the necessary sample size for significant effects of a ketogenic diet on withdrawal, NP or brain functioning in AUD during withdrawal does not exist. Previous behavioral and pharmacological treatment studies in AUD with behavioral, fMRI and MRS as outcome measures have studied on average 20-25 patients per group [treatment versus control: reviewed in 109]. Clinical efficacy of a ketogenic diet in epilepsy was established in randomized-controlled trials in 20 [55] or 94 epilepsy patients [56]. In 20 elderly participants, an acute dose of ketogenic meal improved executive functioning 1.5-3 hours after, as compared to a control meal on a different day [58]. Further, beneficial effects of KD on sleep was established in a study in 18 children with epilepsy [57]. Thus, for within-subject fMRI studies in individuals with AUD sample sizes of 25 patients per group have been effective for obtaining interpretable data regarding behavioral and neurocognitive effects of treatment, suggesting that the sample size of the current protocol is adequate for the identification of effects of ketogenic diet in AUD.

Independent sample t-test will be used to test **Hypothesis 1**, “withdrawal symptom severity within the first week of detoxification will be lower for patients with KD compared to control diet”.

Paired t-test on BOLD signals will be used to test **Hypothesis 2**, “limbic activation to alcohol cues would be reduced after 3 weeks of treatment”; **Hypothesis 3**, “the functional connectivity of the saliency network will be stronger after 3 weeks of treatment”; **Hypothesis 4**, ‘prefrontal cortex atrophy and ventricular enlargement will stronger decrease after 3 weeks of KD treatment compared to control diet’. Assuming a threshold probability for rejecting the null hypothesis (Type I error rate), $\alpha = 0.05$, and a probability of failing to reject the null hypothesis under the alternative hypothesis (Type II error rate), $\beta = 0.2$, the

proposed sample sizes (25 KD versus 25 ND) will allow us to detect an effect size of 0.66.

To test KD treatment effects, mixed ANOVAs will be used to assess whether KD group shows reduced brain activation (Hypothesis 2), higher functional connectivity (Hypothesis 3), and prefrontal cortex atrophy and ventricular enlargement (Hypothesis 4) compared to the control diet group. Assuming $\alpha = 0.05$ and $\beta = 0.2$, the proposed sample sizes will allow us to detect an effect size of 0.9.

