Pearson correlation will be used to test **Hypothesis 5**, “acetone and β -hydroxybutyrate concentration in the anterior cingulate and frontal white matter will increase linearly as a function of time week #1, #2 and #3”. Assuming $\alpha = 0.05$ and $\beta = 0.2$, the proposed sample sizes will allow us to detect statistically significant correlation coefficients, $r > 0.6$.

From our past experience with neuroimaging of patients with AUD, it is expected that, even with careful screening and preparation, approximately 50% of participants will not be able to complete protocols with neuroimaging like the current one being proposed. Thus, we are proposing to recruit 100 participants in order to complete studies in 50 of them (25 on KD and 25 on SA diet).

* We expect that more than 25 patients per group will finish the first week of KD and its assessment of withdrawal symptoms, and will therefore include all patients who finished these assessments to test Hypothesis 1.

11. Human Subjects Protection

a. Subject selection

Adults who fulfill the eligibility criteria will be included, regardless of race, ethnicity, sex, or religious affiliation. We predict the racial composition is approximately 60% Caucasian, 35% African American, and remaining 5% proportion of Asian or other. We predict the Hispanic ethnicity to be approximately 25%. On the same basis, the expected breakdown is 70% male and 30% female. The age range of 18 years and older will provide a sample size that hits our target inclusion criteria of a minimum of 5 year of heavy drinking history.

b. Justification for exclusion of children

Children are excluded since it is unlikely that they will meet the ten-year criteria of heavy drinking required for the study.

c. Justification for exclusion of other vulnerable subjects

Vulnerable populations such as those who lack capacity to consent, are also excluded due to the likely inability to follow instructions for tasks to be performed during diet (KD or SA meal/shake protocol) randomization, MR scans and NP

testing. We also exclude individuals with major psychiatric disorders since this may affect brain function and structure, and may influence study results.

d. Justification for sensitive procedures

N/A

e. Safeguards for vulnerable populations and sensitive procedures

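### Hypothesis 5, the only numbered MRS hypothesis, correlates brain ketones with week and makes no diet comparison, so its result cannot be attributed to the ketogenic diet

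*Combined protocol and SAP*

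**What the plan says.** Section 10.b (Power analysis) states for Hypothesis 5: "Pearson correlation will be used to test" whether acetone and beta-hydroxybutyrate in the anterior cingulate and frontal white matter "will increase linearly as a function of time week #1, #2 and #3". With alpha 0.05 and beta 0.2, it adds that the sample sizes "will allow us to detect statistically significant correlation coefficients" above 0.6.

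The between-arm tests in the same section stop short of this hypothesis. The sentence that begins "To test KD treatment effects, mixed ANOVAs will be used to assess whether KD group shows reduced brain activation (Hypothesis 2" goes on to Hypotheses 3 and 4 and does not mention 5. Hypothesis 1 is a two-group t-test on withdrawal severity.

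In section 10.a the MRS paragraph covers software and output ("These will be used to calculate ratios, such as GABA/Cr, NAA/Cr and, NAA/Cho"). The ghrelin paragraph, by contrast, states an arm comparison: "Ghrelin levels will be compared between KD and SA group". Section 4.e.1 plans to relate blood ketones to brain ketones, again without an arm comparison.

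Section 2.a makes the diet's effect on MRS part of the primary objective, and section 9.a lists MRS neurochemistry among the primary outcomes. Neither singles out ketones.

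**The concern.** Hypotheses 1 to 4 cover withdrawal, cue activation, connectivity and structure, so Hypothesis 5 is the only numbered hypothesis that uses MRS. Its test leaves the randomised control arm with no defined role. A correlation with week mixes the diet effect with whatever happens to brain ketones during three weeks of abstinence.

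The protocol gives reasons to doubt that the untreated course is flat. Section 1 cites rodents under chronic alcohol with raised blood ketones, which might fall with abstinence. Section 4.e gives the SA arm the same ketogenic snacks. Neither tells us the size or direction of any drift.

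Timing adds a second problem. Section 4.e.1 randomises on admission day 1 or 2, and section 4.e places the first scan on days 2-6. Diet start is not dated, but section 4.e.5 places a craving questionnaire before diet initiation and then on MRI days, and the section 22 table marks only the first ketone and ghrelin blood tests as pre-diet. The first scan is thus probably on diet for many participants, and a rise already present then is lost to a week trend.

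As written, the test can be positive without a diet effect and negative despite one.

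**Working it through.** **1. The plan's own figure.** Inputs from section 10.b: alpha 0.05 (two-sided assumed; the plan does not say), power 0.80, 25 per arm. For a Pearson correlation, Fisher's z gives r = tanh[(1.960 + 0.842)/√(n − 3)].

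- n = 25: tanh(2.802/√22) = tanh(0.597) = 0.535
- n = 20: tanh(2.802/√17) = tanh(0.679) = 0.591

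So r > 0.6 is not reproduced from 25 independent pairs. The section's other two detectable effects, checked with the noncentral t, behave alike.

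| Stated in 10.b | n = 20 | n = 25 |
|---|---|---|
| paired effect 0.66 | 0.660 | 0.584 |
| two-group effect 0.9 | 0.909 | 0.809 |
| r > 0.6 | 0.591 | 0.535 |

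All three fit 20 per group, not 25. The slip understates sensitivity and does not threaten the sample size.

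**2. What the Hypothesis 5 test does.** The documents give no drift, effect size or within-person correlation, so the following are assumptions: 25 per arm, three scans, complete data, total SD 1, random intercept with within-person correlation (ICC) 0.3, 0.5 or 0.7, 20,000 simulated trials. Ranges run over the three ICC values; entries are the percentage significant at two-sided 5%.

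*Same rise in both arms, no diet effect:*

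| Rise by week 3 | Pearson, KD scans | Pearson, both arms | One slope per KD participant | KD-SA contrast |
|---|---|---|---|---|
| 0.25 SD | 3-10 | 11-20 | 17-34 | 5 |
| 0.5 SD | 37-40 | 73-83 | 53-87 | 5 |
| 1 SD | 97-100 | 100 | 98-100 | 5 |

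Hand check of the 0.5 SD row, one slope per KD participant: the SD of the week 3 − week 1 change is √[2(1 − ICC)], or 1.183 at ICC 0.3 and 0.775 at ICC 0.7. The noncentrality is 0.5 × √25 / SD = 2.11 and 3.23, giving power of 53% and 87%. Using one value per person does not cure the problem; only a diet term does.

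*A real diet effect of 1 SD at week 3:*

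| Scenario | Pearson, KD scans | Diet × week change | Week-3 KD-SA |
|---|---|---|---|
| None of it present at scan 1 | 97-100 | 83-99 | 93 |
| Half present at scan 1 | 37-40 | 31-61 | 93 |
| All present at scan 1 | 0.1-2 | 5 | 93 |
| None at scan 1, with a 0.5 SD fall in both arms | 37-41 | 83-99 | 94 |

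In the last scenario the Pearson test on both arms pooled is significant in 0-1%. Hand check of the last column: d = 1 with 25 per arm has noncentrality 1 × √(25/2) = 3.54, which gives power 93%.

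**3. Repeated scans.** With no trend, the pooled Pearson test rejects in 0.1-2% under a random intercept alone, and in 6-10% if individual slopes vary with SD 0.8 per week. The error has no fixed direction.

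**4. Limit of the KD-SA contrast.** Section 4.e.3 removes KD participants with ketone-negative urine; SA has no matching rule. Assume no diet effect, removal of the lowest 10, 20 or 30% of KD on a marker correlated 0.5 with brain level, and analysis of those remaining. The week-3 difference then shifts by about 0.10, 0.17 and 0.25 SD, and rejection rises to 7, 9 and 15%. With correlation 0.7 it is 8, 14 and 26%.

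**The case against.** The best counter-argument is that a KD-SA comparison was intended and merely left unwritten. Just after the MRS paragraph, section 10.a promises to adjust for severity or age if the groups differ, which presupposes group analyses. That is fair as to intent, but the sentence supplies no diet term for Hypothesis 5, and the section 10.b list of diet tests leaves it out.

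The drift percentages also depend on assumptions. The rodent evidence points, if anywhere, to a fall, and only the shared snacks suggest a rise. This stands: the percentages show what the test can do, not what will happen here. The attribution problem holds in either direction.

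The repeated-scans point is secondary. With modest slope variation the pooled test stays conservative or close to nominal: at slope SD 0.5 per week it rejects in 2.1 to 5.4%. Attribution to diet does not turn on this.

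The KD-SA contrast is not clean either, because of the KD-only removal rule; step 4 shows the size. Disclosure does not remove that bias, but the within-KD trend faces the same selection and has no control arm.

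Lastly, Hypothesis 5 has four outcomes (two metabolites, two regions). A detectable d of 0.81 applies to each outcome singly, as r > 0.6 did. With Bonferroni for four it would be 0.98, and power at 0.81 would be 61%.

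**Conclusion.** The concern holds and should be fixed. Followed as written, the only numbered MRS test cannot answer the primary question about the diet, because it contains no diet comparison and no other section provides one for brain ketones. This follows from the text alone. The size is illustrative: under the stated assumptions a moderate shared drift of 0.5 SD gives a significant result in 37-87% of trials with no diet effect, depending on how the scans are entered. A 1 SD diet effect established by the first scan is almost always missed. Confidence is medium, because drift, diet start relative to scan 1 and within-person correlation are not given. The detectable-effect mismatch is a minor, conservative slip.

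**What to change.** Replace the Pearson test for Hypothesis 5 with a mixed model on all available scans of both arms: diet, week as a category, and diet × week, with unstructured within-person covariance or robust standard errors rather than a random intercept alone. Include scans taken before any compliance withdrawal. Pre-specify the KD-SA contrast. The week-3 difference is suggested because it does not need scan 1 to be pre-diet. Report diet × week and the within-KD trend beside it, which keeps the question of a rise over time. State that KD-only removal for ketone-negative urine makes a comparison among those remaining not fully randomised, and say how the four outcomes are handled.

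Correct section 10.b for 25 per arm at 80% power and two-sided 5%. Where it now says "proposed sample sizes (25 KD versus 25 ND) will allow us to detect an effect size of 0.66", the paired figure is 0.58. Where it says "the proposed sample sizes will allow us to detect an effect size of 0.9", the two-group figure is 0.81, if a standardised mean difference is meant. For Hypothesis 5, give d = 0.81 per outcome in place of r > 0.6. The methods for Hypotheses 2 to 4 need no change on this account.

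The cost is SAP wording and a standard model, with no new scans. If ketones are unaffected at scan 1 and rise linearly only in KD, the week-3 contrast gives up a little power against a within-person KD trend (93% versus 98-100% for a 1 SD rise). With large slope variation (SD 0.8 per week) its power falls to about 77%.

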age will be used to determine how many calories are provided to each participant. While on the KD/SA diet, patients are limited to drink non-caloric drinks (water, diet soda, coffee and tea without milk or sugar). In addition to the diets, MRI/fMRI/MRS scans, genetic tests, self-report ratings, motor activity, sleeping behavior, NP testing and personality measures will be obtained in all participants. The first MRI session and the first NP testing will be performed within the first 2-6 days of admission. The MRI sessions will be repeated on a weekly basis (second and third week of hospitalization; the later corresponding to the last week of their inpatient stay) and the NP testing will be repeated during the third week of hospitalization. MRI scanning session and NP tests are described below and are for research purpose only.

During the inpatient period, participants will be periodically monitored for signs of withdrawal and evaluated for mood, sleep and alcohol cravings. Compliance with diet adherence (KD or SA) will be closely monitored during the hospital stay using daily urine tests.

After the final MRI sessions, the study diets are discontinued and the individual blind will be broken on a per subject basis. If KD is discontinued this will be done by slowly increasing the levels of carbohydrates to the diets of the SA group [68]. The levels of carbohydrates in the control group remains constant throughout the study, but patients are still blind to treatment group.

Participants will then be released at about 3-4 weeks from the Clinical Center and will have a 3 month follow up period under this protocol which is discussed below in section 4.d.12 *Follow-Up*.

1. Ketogenic Diet (KD) / Standard American (SA) Snacks and Shakes: Participants will be randomized to a meal plan of either a ketogenic diet (KD) or standard American (SA) diet at the time they sign the consent (day 1 or 2 of admission). For each meal at breakfast, lunch and dinner, the diets will consist of SA meal (carbohydrate rich) or KD meal depending on treatment randomization. Compliance tests are done daily with urine tests measuring ketone levels by an independent person (BSN RN) [69], results of which are retained. To ensure that the diet is double blind in both the outpatient and inpatient phases, solid snacks are always ketogenic and shakes are either KD or SA.

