2. **Randomization and blinding:** The study has a blinded and randomized design. A randomization code will be generated prior to recruiting and patient randomization will be assigned accordingly. Since we expect a larger dropout in the KD group, we pre-set the ratio of KD:SA participants as 3:2 in the randomization generation.* Nurses and research staff who do CIWA, craving ratings and other study procedures with patients will not have access to the randomization key. An independent person (BSN RN) will perform and analyze daily ketone testing and blood pricks and will have access to the key. The nutrition department also has access to the randomization key to prepare the diets, but patients' diets will be sent out without information on its contents.* This ratio will be set for the first 20 participants. After the enrollment of 20 participants, the ratio will be evaluated by an independent person (BSN RN) based on diet compliance during their 3 weeks inpatient stay as per questionnaire and urine screen. Results are shared with the PI who will modify the ratio if needed to aim for a 50% KD versus 50% SA study completion.
3. **Diet Compliance:** In addition to daily urine tests (described above in section 4.e.1) and blood pricks, a daily questionnaire on whether additional food was consumed and whether the participant was compliant will be assessed by an independent person (BSN RN). On each day, participants will be asked if they were compliant to the diet (i.e. the shakes and snacks provided), or if additional food was consumed. If yes, which food items and at what time. At that time, they will also be encouraged to be compliant with the diet. All participants will be motivated on a daily basis to be compliant to their diet by nutrition department staff. If after the first 3 days of diet initiation a participant (in either KD or SA) self-reports non-compliance to the diet for 4

days, the PI will be informed and participant will be withdrawn and excluded from further study participation.

Additionally, if after the first 5 days of diet initiation, a participant in the KD group has 3 urine tests that are negative for ketone bodies, this participant will also be removed from the study. In this case, the independent person who monitors daily urine testing, will inform study staff about the compliance breach and the patient will be removed from the study.

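### Hypothesis 5 tests brain ketones only as a linear rise over weeks 1–3, with no pre-diet MRS and no KD-versus-SA test, so its result depends on when scan 1 falls after diet start

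*Combined protocol and SAP*

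**What the plan says.** Section 10.b states Hypothesis 5 as a rise in acetone and beta-hydroxybutyrate, in the anterior cingulate and frontal white matter, that will "increase linearly as a function of time week #1, #2 and #3". The method sentence begins "Pearson correlation will be used to test". It gives neither the unit of analysis (patients or patient-scans) nor the arm or arms used. It adds that correlations above 0.6 are detectable at alpha 0.05 and beta 0.2. The target is to "complete studies in 50 of them (25 on KD and 25 on SA diet").

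Timing comes from section 4.e. Patients are randomized to a diet "at the time they sign the consent (day 1 or 2 of admission"). "The first MRI session and the first NP testing will be performed within the first 2-6 days of admission", and MRI is repeated in the second and third weeks. Section 4.a allows these time points to move for practical reasons.

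Three places indicate that scan 1 is an on-diet scan:
- Section 4.e.3 counts first-week MRI among the data on KD effects.
- Section 4.e.5 lists a pre-diet craving rating separately from the ratings on MRI days.
- The only pre-diet ketone measure in the section 22 schedule is a blood test.

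Section 10.b names mixed ANOVAs against the control diet for Hypotheses 2, 3 and 4 only. Apart from Hypothesis 5, brain ketones appear in the analysis plans only in section 4.e.1, which relates MRS ketones to blood ketones.

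**The concern.** A slope on week number measures the diet's effect only if scan 1 stands in for the pre-diet state. Here it does not. Any rise completed before scan 1 drops out of the slope, so a diet that raises brain ketones quickly scores lower than one that raises them slowly to the same level.

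The protocol gives reasons to expect an early effect. The compliance rule in section 4.e.3 applies "if after the first 5 days of diet initiation, a participant in the KD group has 3 urine tests that are negative for ketone bodies". Hypothesis 1 predicts less severe withdrawal within the first week, and the précis attributes the expected benefit to raised acetate in the brain.

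MRS is a primary objective (section 2.a) and a primary outcome (section 9.a). Hypothesis 5 is the only stated hypothesis on brain ketones. As written, its result mixes the size of the diet effect with the scan schedule, and no specified comparison with the control diet separates the two.

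**Working it through.** **The plan's own figure.** The detectable correlation by Fisher's z is r = tanh[(1.960 + 0.842)/√(n − 3)], two-sided alpha 0.05, 80% power:
- n = 20: 0.591
- n = 25: 0.535
- n = 50: 0.387
- n = 75 (25 patients × 3 scans, treated as independent): 0.319

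The stated 0.6 is close to n = 20 and does not follow from n = 25. That difference is conservative, and the point here does not rest on it.

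**Diet days at scan 1.** Start is admission day 1 or 2 and scan 1 is day 2–6. The difference runs from 2 − 2 = 0 to 6 − 1 = 5 days. Same-day diet start is an assumption, since no separate start day is given.

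**What the slope measures.** Let the plateau be 1, let scan 1 be at fraction f of it, and let scans 2 and 3 be at the plateau. The least-squares slope on week is (1 − f)/2. The diet effect at sessions 2 and 3 is 1 whatever f is. With between- and within-patient SDs b and w, and ignoring the spread of f between patients, the expected pooled correlation is approximately

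r ≈ [(1 − f)/3] / {√(2/3) × √[b² + w² + (2/9)(1 − f)²]}.

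For f = 0.5 and b = w = 0.5, this is 0.1667/(0.8165 × 0.7454) = 0.27.

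**Simulation.** Assumptions not in the documents: a linear ramp to plateau; start and scan days uniform over their windows; later scans 7 and 14 days after scan 1; b and w each 0.3–0.7 of plateau. There are 25 KD patients. Power means a significant positive result. Pooled Pearson uses all 75 points; the within-patient test is a t-test on session 3 minus session 1.

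| Plateau by diet day | Mean level at scan 1 | Mean pooled r | Power, pooled Pearson | Power, within-patient |
|---|---|---|---|---|
| 2 | 80% | 0.08–0.17 | 2–28% | 14–43% |
| 3 | 70% | 0.12–0.25 | 10–63% | 27–76% |
| 5 | 50% | 0.20–0.40 | 37–99% | 63–100% |

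With a day-5 plateau and uniform timing, 10% of patients are at plateau at scan 1.

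**Moving only scan 1.** Plateau by diet day 5, b = w = 0.5:

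| Scan 1, admission day | Mean level | Power, pooled Pearson |
|---|---|---|
| 2 | 10% | about 100% |
| 3 | 30% | about 98% |
| 4 | 50% | about 74% |
| 5 | 70% | about 26% |
| 6 | 90% | 2–3% |

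The diet effect is identical in every row. On day 6 the within-patient test reaches only about 10%.

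**Comparison between diets.** The mean of sessions 2 and 3, 25 KD against 25 SA with SA set to 0, has power 98–100% for the plateau times tabulated. At the least favourable SDs (0.7 and 0.7) the standardized difference is 1/√(0.49 + 0.49/2) = 1.17. High power is therefore built into the assumed effect size. The relevant result is that it does not depend on scan 1.

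**The case against.** The strongest reply is that the documents do not say brain ketones plateau by day 5. The rule in section 4.e.3 concerns urine strips that detect acetoacetate. It sets a presence-or-absence floor for compliance, not a peak, and levels could keep rising after ketones become detectable. If the brain rise took a week or more, the trend test would do well: a ramp to day 7 gives about 64–100% power under the same assumptions. This stands, and it is why the point is conditional.

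A reader might infer that a fast, full diet effect must test as null. The documents do not support that. Even with a plateau at day 5, scan 1 averages half the plateau, and the low-high-high pattern still correlates positively with week. Near-null results need a plateau by about diet day 1–2, or first scans late in the window.

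A reader might also count simulated correlations below 0.6 as failures. The 0.6 is a detectable correlation, not a success criterion; with 75 points, significance needs only |r| of about 0.23.

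Part of the loss is a separate fault: pooling repeated scans lets between-patient spread dilute r. A within-patient test recovers part of it, but it still depends on scan day.

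Finally, the planned correlation of MRS with blood ketones in section 4.e.1 means Hypothesis 5 is not the only brain-ketone analysis. That correlation is not a test of diet, so the gap remains. For the same reason, it goes too far to predict that a null result would be read as the diet not reaching the brain.

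**Conclusion.** The concern holds in conditional form. The documents establish that Hypothesis 5 is a week trend, that scan 1 falls about 0–5 days after randomization, that no pre-diet MRS is listed, and that no KD–SA test of brain ketones is specified. It follows by arithmetic that the trend shrinks in proportion to the share of the rise completed by scan 1.

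How much power this costs rests on assumed kinetics and variances. The loss ranges from negligible (slow rise, early scans, small SDs) to nearly complete (fast rise or late first scans). The dependence on scan day does not need a very fast plateau: it appears in full with a plateau at diet day 5 and scan days the protocol permits. The sponsor should change the analysis, but the material does not show that the test as planned would fail.

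**What to change.** Restate Hypothesis 5 as higher brain acetone and beta-hydroxybutyrate on KD than on SA. Test it in a repeated-measures model with diet, scan and diet-by-scan terms, entering scan as a category or as days since diet start. Make the KD–SA difference at sessions 2 and 3 the main contrast. Record diet start so that diet days at each scan are known, and report the time course descriptively. Remove the word linearly and the Pearson detectable-correlation statement for this hypothesis.

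The cost is analysis wording only, with the same scans and patients. The small downside is that the linear trend is no longer the formal test.
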